#### 5.1. Inclusion Criteria

A subject will be eligible for inclusion in this study only if all of the following criteria apply:

AGE
1. Between 18 and 75 years of age inclusive, at the time of signing the informed consent.
TYPE OF SUBJECT AND DIAGNOSIS INCLUDING DISEASE SEVERITY
2. Subjects that do not have any medical conditions, other than moderate to severe RA, that in the opinion of the Investigator put the subject at unacceptable risk or interfere with study assessments or integrity of the data. These medical conditions should be

stable at the time of screening and are expected to remain stable for the duration of the study.
 
 
3. Subject has had a confirmed diagnosis of rheumatoid arthritis according to the revised 2010 American College of Rheumatology/European League Against Rheumatism ACR-EULAR classification criteria.
 
4. Disease duration of <math>\geq 12</math> weeks (time from onset of patient-reported symptoms of either pain or stiffness or swelling in hands, feet or wrists) at screening.
 
5. Swollen joint count of <math>\geq 4</math> (28-joint count) and tender joint count <math>\geq 4</math> (28-joint count) at screening.
 
6. Subject has a DAS28 CRP disease activity score of <math>\geq 3.2</math> and CRP <math>\geq 5.0</math> mg/L (<math>\geq 4.76</math> nmol/L) at screening.
 
7. Subject must have received at least 12 weeks of non-biologic DMARD monotherapy or methotrexate (MTX)/DMARD combination therapy prior to screening AND must be on stable dose throughout the study.
 
8. Subject is naive to any biological therapies for RA
 
 
OR
 
Subject may have had previous exposure to a single anti-TNF biologic agent which was discontinued for reasons other than primary non-response more than 8 weeks (or 5 half lives whichever is longer) from first dose. Note: Exposure to a single anti-TNF is not required in addition to Inclusion #7 above.
 
 
9. For subjects who have consented to synovial joint biopsy: 
 
a. Subject has an involved knee, wrist, or ankle suitable for biopsy, as assessed by a rheumatologist at screening.
 
 
 

--

WEIGHT
---------------

10. A body mass index (BMI) within range of 18.5 - 35 kg/m  (inclusive) at screening.
---

SEX
------------

11. Male and female subjects
------------------------------

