#### 7.3.6. Clinical Safety Laboratory Assessments

All protocol required laboratory assessments, as defined in Table 3, must be conducted in accordance with the Laboratory Manual, and Protocol Time and Events Table (Section 7.1). Laboratory requisition forms must be completed and samples must be clearly labelled with the subject number, protocol number, site/centre number, and visit date. Details for the preparation and shipment of samples will be provided by the laboratory and are detailed in the laboratory manual. Reference ranges for all safety parameters will be provided to the site by the laboratory responsible for the assessments.

If additional non-protocol specified laboratory assessments are performed at the institution's local laboratory and result in a change in subject management or are considered clinically significant by the Investigator (e.g., SAE or AE or dose modification) the results must be recorded in the CRF.

Refer to the laboratory manual for appropriate processing and handling of samples to avoid duplicate and/or additional blood draws.

All study-required laboratory assessments will be performed by a central laboratory, apart from:

- Haematology, platelets and coagulation sample if they are required to be taken closer to the biopsies (as per local practices) than specified in Section 5.4.5.

**NOTE:** Local laboratory results are only required in the event that the central laboratory results are not available in time for either a treatment and/or response evaluation to be performed. If a local sample is required, it is important that the sample for central analysis be obtained at the same time. Additionally, if the local laboratory results are used to make either a treatment or response evaluation, the results must be entered into the CRF.

Haematology, clinical chemistry, urinalysis and additional parameters to be tested are listed in [Table 3](#).

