### 5. SELECTION OF STUDY POPULATION AND WITHDRAWAL CRITERIA

Specific information regarding warnings, precautions, contraindications, adverse events, and other pertinent information on the GSK investigational product (IP) or other study treatment that may impact subject eligibility is provided in the IB [GlaxoSmithKline Document Number [2014N204126\\_01](#)].

In addition, Investigators are expected to follow local and/or national guidelines with respect to vaccinations, including vaccinations for influenza and pneumococcus, in subjects with RA.

Deviations from inclusion and exclusion criteria are not allowed because they can potentially jeopardize the scientific integrity of the study, regulatory acceptability or subject safety. Therefore, adherence to the criteria as specified in the protocol is essential.

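### The CRP entry threshold is printed in two units that disagree by a factor of about 7.5 to 10, so inclusion criterion 6 sets two different cut-offs

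*Protocol*

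**What the plan says.** Protocol Section 5.1, criterion 6, combines a DAS28-CRP score of at least 3.2 with a CRP minimum: "CRP \geq 5.0 mg/L ( \geq 4.76 nmol/L) at screening". The bracket reads as a unit conversion. The protocol uses brackets the same way in exclusion criterion 23 (Section 5.2), where white cell and platelet limits appear per mm³ or per µL and then per litre.

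The introduction to Section 5 leaves no tolerance on eligibility: "Deviations from inclusion and exclusion criteria are not allowed because they can potentially jeopardize the scientific integrity of the study".

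Section 7.3.6 says where the tests are run: "All study-required laboratory assessments will be performed by a central laboratory, apart from" certain haematology, platelet and coagulation samples taken close to a biopsy. CRP is listed in Table 3 of that section. Neither place gives the unit in which CRP is reported, and the document contains no molar mass or conversion factor for CRP.

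**The concern.** A criterion that states one threshold in two units works only if the two figures describe the same concentration. If they do not, a reader applying one unit and a reader applying the other will classify some subjects differently, and each can say the protocol was followed.

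The stake is the definition of the study population. CRP is an entry criterion in its own right, and Section 7.4.2 makes it a component of DAS28, ACR response and Vectra DA. With approximately 24 subjects planned on the three-times-daily regimen and at most 18 on the twice-daily regimen (Section 9.2.1), it should be possible to say unambiguously which screening CRP values qualify. As printed, criterion 6 cannot be audited consistently.

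**Working it through.** **Inputs**
- Mass threshold: 5.0 mg/L (Section 5.1, criterion 6).
- Molar threshold: 4.76 nmol/L (same line).
- Molar mass of CRP: not in the documents. Assumed range 105 to 140 kDa for the whole molecule; 21 to 25 kDa for a single subunit is tried as a check.

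**Formula**

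nmol/L = (mg/L × 1,000) ÷ molar mass in kDa

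**Step 1: what the printed pair implies**

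5.0 × 1,000 ÷ 4.76 = 1,050 kDa. The printed equivalence holds only at this molar mass, which is 7.5 to 10 times the assumed range.

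**Step 2: convert each figure over the assumed range**

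| Assumed molar mass (kDa) | 5.0 mg/L in nmol/L | Ratio to 4.76 | 4.76 nmol/L in mg/L |
|---|---|---|---|
| 105 | 47.6 | 10.0 | 0.50 |
| 115 | 43.5 | 9.1 | 0.55 |
| 125 | 40.0 | 8.4 | 0.60 |
| 140 | 35.7 | 7.5 | 0.67 |

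The stated 4.76 nmol/L is not reproduced at any mass in the range.

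**Step 3: does another molar mass or mass unit rescue the bracket?**
- Single subunit, 21 to 25 kDa: 5.0 mg/L becomes 238 to 200 nmol/L, a gap of 50- to 42-fold. This is worse.
- 5 mg/dL at 105 kDa: 476 nmol/L. No match.
- 0.5 mg/dL is the same concentration as 5.0 mg/L. No match.
- 0.5 mg/L at 105 kDa: 0.5 × 1,000 ÷ 105 = 4.76 nmol/L. This matches.

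The digits of the bracket therefore fit a molar mass of 105 kDa with the decimal point one place out. The arithmetic alone does not show which of the two numbers carries the slip.

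**Step 4: check that the brackets are meant as equivalents**

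In exclusion criterion 23, 3,000 per mm³ × 10⁶ mm³ per litre = 3.0 × 10⁹ per litre, and 100,000 per µL × 10⁶ µL per litre = 100 × 10⁹ per litre. Both agree with the printed brackets. The CRP bracket does not.

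**Step 5: who is affected**

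Subjects with screening CRP from about 0.5–0.7 mg/L up to just under 5.0 mg/L, who also have a DAS28-CRP of at least 3.2 and at least 4 swollen and 4 tender joints, pass on the nmol/L figure and fail on the mg/L figure.

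**The case against.** Several points on the other side carry weight.

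- **Version.** The Section 5.1 shown belongs to the twice-daily version, and four amendments followed. The amended Section 5.1 is not shown, parts of the amendment logs are not shown either, and Amendments 1 to 3 each mention other minor clarifications. A later correction cannot be excluded. What can be said is that no visible change list touches criterion 6; the Section 5.1 change shown under Amendment 3 concerns criterion 11. This limits the point but does not remove it.
- **Outside figure.** The check needs a molar mass that the protocol does not give. That is why a range is used. The mismatch survives the whole range, but an exact factor of ten and a corrected value of 47.6 nmol/L hold only at its 105 kDa end.
- **Use of the molar figure.** The mg/L figure comes first, CRP is measured centrally, and local results are needed only when central ones are late, with a central sample taken in parallel. Nothing shows that any site or the laboratory works in nmol/L.
- **Other gates.** The DAS28-CRP and joint-count minima still apply, so the molar figure alone admits nobody.

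A reader might infer that patients with very low CRP were enrolled and had little room to improve on the efficacy endpoints. The documents do not support this. They give no evidence that the nmol/L figure was used. CRP is one of four DAS28 components, and ACR response requires both joint counts plus three of five other measures, so it can be reached with no change in CRP. The primary objective is safety and tolerability, with no formal hypothesis, and the primary analysis does not turn on the CRP minimum.

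**Conclusion.** The point stands as an internal inconsistency in an eligibility threshold. In the only Section 5.1 available, the mass and molar figures for the CRP minimum differ by a factor of 7.5 to 10 for an assumed molar mass of 105 to 140 kDa, and no molar mass tried brings them together. A misplaced decimal is the likely explanation, but this is an inference from the matching digits at 105 kDa. The documents do not settle which figure was intended.

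The realised effect is unknown. It could be nil if eligibility was always judged on central results in mg/L. It would be a real difference in who qualifies if nmol/L was used anywhere. It is still worth correcting because the criterion allows no deviations and, as written, cannot be applied in only one way.

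**What to change.** 1. Confirm whether the amended Section 5.1 still carries both figures.
2. If it does, reconcile them. Either delete the nmol/L figure, or replace it with the central laboratory's own molar equivalent of the intended threshold. If 5.0 mg/L is what was intended, that will fall at about 36 to 48 nmol/L, depending on the laboratory's factor.
3. State in criterion 6 the unit in which CRP is judged for eligibility.
4. Ask the central laboratory and sites whether CRP was ever reported or judged in nmol/L. Only if it was, list enrolled subjects' screening CRP against the intended threshold.

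The cost is one number and a short clause in Section 5.1, one query to the laboratory and sites, and, if needed, one listing of screening values already held. No analysis changes.

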**Males:**

Male subjects with female partners of child bearing potential must comply with the following contraception requirements in [Appendix 6](#).

**Females:**

A female subject is eligible to participate if she is not pregnant (as confirmed by a negative serum human chorionic gonadotrophin [hCG] test), not lactating, and at least one of the following conditions applies:

- a. Non-reproductive potential as defined in [Appendix 6](#).
- b. Reproductive potential and agrees to follow one of the options listed in the Modified List of Highly Effective Methods for Avoiding Pregnancy in Females of Reproductive Potential (FRP) (see [Appendix 6](#)) from 30 days prior to the first dose

of study medication and until at least 30 days after the last dose of study medication and completion of the follow-up visit.

The Investigator is responsible for ensuring that subjects understand how to properly use these methods of contraception.

#### INFORMED CONSENT

12. Capable of giving signed informed consent as described in Section 10.2 which includes compliance with the requirements and restrictions listed in the consent form and in this protocol.

## 5.2. Exclusion Criteria

A subject will not be eligible for inclusion in this study if any of the following criteria apply:

#### CONCURRENT CONDITIONS/MEDICAL HISTORY (INCLUDES LIVER FUNCTION AND QTc INTERVAL)

1. Subject with a positive anti-double stranded deoxyribonucleic acid (DNA [anti-dsDNA]) and confirmed diagnosis of systemic lupus erythematosus (SLE).
2. Subject with current history of Suicidal Ideation Behaviour (SIB) as measured using the Columbia Suicide Severity Rating Scale (C-SSRS) or a history of attempted suicide.
3. An active infection, or a history of infections as follows:
  - Hospitalisation for treatment of infection within 60 days before first dose (Day 1).
  - Currently on any suppressive therapy for a chronic infection (such as pneumocystis, cytomegalovirus, herpes simplex virus, herpes zoster and atypical mycobacteria).
  - Use of parenteral (IV or intramuscular) antibiotics (antibacterials, antivirals, antifungals, or antiparasitic agents) for an infection within 60 days before first dose.
  - A history of opportunistic infections within 1 year of screening (e.g. pneumocystis jirovecii, CMV pneumonitis, aspergillosis). This does not include infections that may occur in immunocompetent individuals, such as fungal nail infections or vaginal candidiasis, unless it is of an unusual severity or recurrent nature.
  - Recurrent or chronic infection or other active infection that, in the opinion of the Investigator might cause this study to be detrimental to the patient.
  - History of TB, irrespective of treatment status.
  - A positive diagnostic TB test at screening defined as a positive QuantiFERON-TB Gold test or T-spot test. In cases where the QuantiFERON or T-spot test is indeterminate, the subject may have the test repeated once, but they will not be eligible for the study unless the second test is negative. In cases where the QuantiFERON or T-spot test is positive, but a locally-read follow up chest x-ray, shows no evidence of current or previous pulmonary

tuberculosis, the subject may be eligible for the study at the discretion of the Investigator and GSK Medical Monitor.

4. QTc > 450msec or QTc > 480msec for subjects with bundle branch block at screening.

The QTc is the QT interval corrected for heart rate according to either Bazett's formula (QTcB), Fridericia's formula (QTcF), or another method, machine or manual over read.

The specific formula that will be used to determine eligibility and discontinuation for an individual subject should be determined and documented prior to initiation of the study. In other words, several different formulae cannot be used to calculate the QTc for an individual subject and then the lowest QTc value used to include or discontinue the subject from the trial. For purposes of data analysis, QTcB, QTcF, another QT correction formula, or a composite of available values of QTc will be used as specified in the Reporting and Analysis Plan (RAP).

5. ALT >2xULN and bilirubin >1.5xULN (isolated bilirubin >1.5xULN is acceptable if bilirubin is fractionated and direct bilirubin <35%) at screening.
6. Current active or chronic history of liver or biliary disease (with the exception of Gilbert's syndrome or asymptomatic gallstones).
7. Current or history of renal disease or estimated glomerular filtration rate (GFR) by Chronic Kidney Disease Epidemiology Collaboration equation (CKD-EPI) calculation <60 mL/min/1.73m^2 at screening.
8. Hereditary or acquired immunodeficiency disorder, including immunoglobulin deficiency.
9. A major organ transplant (e.g., heart, lung, kidney, liver) or hematopoietic stem cell/marrow transplant.
10. Any planned surgical procedures including surgical joint procedures (e.g., intra-articular, tendon sheath, or bursal corticosteroid injections) during the study.
11. A history of malignant neoplasm within the last 5 years, except for adequately treated non-metastatic cancers of the skin (basal or squamous cell) or carcinoma in situ of the uterine cervix that has been fully treated and shows no evidence of recurrence.
12. Has undergone surgery including synovectomy or arthroplasty on the joint chosen for biopsy and/or magnetic resonance imaging (MRI).
13. The subject has a history of any other joint disease other than RA at the knee, wrist or ankle joint chosen for biopsy and/or MRI (e.g., gout, pseudogout, osteoarthritis).
14. Has undergone intra-articular corticosteroid injection, arthrocentesis or synovial biopsy on any joint within 6 weeks of screening.
15. A known allergy to lidocaine or other local anaesthetics (**Note**: only applies to subjects who consent for synovial biopsy procedures).
16. Contraindication to MRI scanning (as assessed by local MRI safety questionnaire) which includes but are not limited to:
  - Intracranial aneurysm clips (except Sugita™) or other metallic objects,
  - History of intra-orbital metal fragments that have not been removed by a medical professional.
  - Pacemakers or other implanted cardiac rhythm management devices and non-MR compatible heart valves,

- Inner ear implants,
- History of claustrophobia which may impact participation.

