[Part 2 of 2 of the document. The other parts are not shown.]

Therapy	Time period
A change in dose of methotrexate or other DMARD.	12 weeks prior to screening until after the follow up visit (Day 112)
Greater than 10mg/day oral prednisolone (or equivalent glucocorticoid) or a change in dose of corticosteroid.	4 weeks prior to screening until after the follow up visit (Day 112)
Intramuscular glucocorticoids (e.g., methylprednisolone ≤120 mg/month)	4 weeks prior to screening until after the follow up visit (Day 112)
Intra-articular corticosteroid injections	6 weeks prior to screening and until after the follow up visit (Day 112).
Janus Kinase (JAK) Inhibitors	4 weeks prior to screening until after the follow up visit (Day 112).
P-glycoprotein (Pgp) inhibitors including but not limited to amiodarone, azithromycin, captopril, carvedilol, clarithromycin, conivaptan, cyclosporine, diltiazem, dronedarone, erythromycin, felodipine, itraconazole, ketoconazole, lopinavir, ritonavir, quercetin, quinidine, ranolazine, ticagrelor, verapamil [FDA, 2012].	4 weeks prior to first dose (Day 1) until after the follow up visit (Day 112).
Narrow therapeutic index (NTI) CYP3A4 substrates including but not limited to alfentanil, astemizole, cisapride, cyclosporine, dihydroergotamine, ergotamine, fentanyl, pimozone, quinidine, sirolimus, tacrolimus, terfenadine [FDA, 2012].	4 weeks prior to the first dose (Day 1) until after the follow up visit (Day 112).
Biologic therapies for the treatment of rheumatoid arthritis not limited to anti-TNF biologics or other biologics, rituximab, anakinra, abatacept or tocilizumab.	At any time.

Exposure to more than one anti-TNF biologic therapies for the treatment of RA including but not limited to anti-TNF biologics, infliximab, adalimumab, etanercept, certolizumab and golimumab.
 
Exception: Exposure to a single anti-TNF-biologic for which the subject discontinued for a reason other than primary non-response is permitted.
	
Cannot have been exposed to more than one anti-TNF biologic or be on at any time during the study.
 
In the case of a single anti-TNF biologic for which the subject discontinued for a reason other than primary non-response, the subject must not be on for 8 weeks or 5 half lives (whichever is longer) prior to first dose until after the follow up visit (Day 112).

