## 4.6.1. Risk Assessment

Potential Risk of Clinical Significance	Summary of Data/Rationale for Risk	Mitigation Strategy
Investigational Product (IP) GSK2982772		
Central Nervous System (CNS) effects	
Non-clinical data: In the 4-week GLP toxicology study, CNS findings were observed in 4/12 monkeys which were administered 100 or 300 mg/kg/day. CNS findings included uncoordination, irregular gait, trembling, hunched appearance, and decreased activity. The clinical relevance of these findings in humans is not known. The NOAEL for this study was determined at 10 mg/kg/day.
 
In the 13-week GLP toxicology study, there were no CNS findings observed in monkeys administered 10, 30 or 100 mg/kg/day. The NOAEL for this study was determined at 30 mg/kg/day.
 
Clinical data: A First Time in Human (FTiH) study with single ascending and multiple ascending dose study has been performed in 67 healthy male volunteers to date. See Investigator's Brochure (IB) [GlaxoSmithKline Document Number 2014N204126_01]. No drug-associated CNS adverse events were identified and no Serious Adverse Effects (SAEs) were reported.
	
Subject Selection:
 
 
Subjects with known history of significant neurologic disorders including but not limited to progressive multiple sclerosis (MS), Amyotrophic lateral sclerosis (ALS), Alzheimer's and dementia will be excluded.
 
Individuals with potentially increased susceptibility for neurologic effects will be excluded based on medical history at screening.
 
 
Subject Monitoring:
 
 
Subjects will be monitored for standard CNS-related adverse events.
 

Immunosuppression	The possibility of immunosuppression, including an increase in the frequency and/or severity of infection, may result from the intended pharmacologic effect of GSK2982772. This may be enhanced in subjects taking other immunomodulating drugs or corticosteroids.	
Subject Selection:
 
 
Subjects with recurrent, chronic or active infections will be excluded from the study.
 
Subjects will be screened for TB, HIV, Hepatitis B and C, and excluded from the study if positive.
 

Potential Risk of Clinical Significance	Summary of Data/Rationale for Risk	Mitigation Strategy

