#### DIAGNOSTIC ASSESSMENTS AND OTHER CRITERIA

23. Haemoglobin <11 g/dL; haematocrit <30%, white blood cell count  $\leq 3,000/\text{mm}^3$  ( $\leq 3.0 \times 10^9/\text{L}$ ) or  $\geq 14,000/\text{mm}^3$  ( $\geq 14 \times 10^9/\text{L}$ ); platelet count  $\leq 100,000/\mu\text{L}$  ( $\leq 100 \times 10^9/\text{L}$ ); absolute neutrophil count  $\leq 3 \times 10^9/\text{L}$ ; lymphocyte count  $< 1 \times 10^9/\text{L}$  at screening.
24. Presence of hepatitis B surface antigen (HBsAg), positive hepatitis C antibody test result at screening or within 3 months prior to first dose of study treatment. As potential for and magnitude of immunosuppression with this compound is unknown, subjects with presence of hepatitis B core antibody (HBcAb) should be excluded.
25. A positive serology for human immunodeficiency virus (HIV) 1 or 2 at screening.
26. Where participation in the study would result in donation of blood or blood products in excess of 500 mL within 3 months.
27. Exposure to more than 4 investigational medicinal products within 12 months prior to the first dose.

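### In the version shown, exclusion 3 can admit a TB-test-positive subject on a clear chest x-ray with no preventive treatment, although Section 4.6.1 counts on such subjects being excluded

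*Protocol*

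**What the plan says.** Section 4.6.1 (Risk Assessment, immunosuppression row) gives this subject-selection measure: "Subjects will be screened for TB, HIV, Hepatitis B and C, and excluded from the study if positive". It states no exception.

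Section 5.2, exclusion criterion 3, treats TB in four steps:
- Any history of TB excludes, treated or not.
- A positive QuantiFERON-TB Gold or T-spot test at screening excludes.
- An indeterminate test may be repeated once, and the subject is ineligible unless the repeat is negative.
- The last step qualifies the second. It begins "In cases where the QuantiFERON or T-spot test is positive, but a locally-read follow up chest x-ray, shows no evidence" of current or past pulmonary disease, and concludes that "the subject may be eligible for the study at the discretion of the Investigator and GSK Medical Monitor".

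The last step sets no condition of preventive treatment, specialist review or TB follow-up. An earlier bullet of the same criterion excludes anyone currently on suppressive therapy for a chronic infection.

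Criterion 24 deals with hepatitis B: "As potential for and magnitude of immunosuppression with this compound is unknown, subjects with presence of hepatitis B core antibody (HBcAb) should be excluded". Section 5 says of the criteria generally that "adherence to the criteria as specified in the protocol is essential".

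**The concern.** The risk section presents exclusion on a positive TB screen as a protection, and the benefit:risk conclusion in Section 4.6.3 rests on the measures taken to minimise risk. Someone who reads only Section 4.6.1 would conclude that no test-positive subject can enter. The operative criterion allows one to enter without treatment.

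The trial population is the one for which Section 4.6.1 is most cautious. It says of possible immunosuppression: "This may be enhanced in subjects taking other immunomodulating drugs or corticosteroids". Background therapy is an entry condition (inclusion 7: "Subject must have received at least 12 weeks of non-biologic DMARD monotherapy or methotrexate (MTX)/DMARD combination therapy prior to screening"). On steroids, the current Table 2 prohibits only "Greater than 10mg/day oral prednisolone (or equivalent glucocorticoid) or a change in dose of corticosteroid", so a stable dose of up to 10 mg/day remains allowed. At stake is the exposure of a test-positive subject, on background DMARDs and possibly steroids, to a compound whose immunosuppressive effect the protocol itself calls unknown.

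**Working it through.** No arithmetic applies. The check compares the two rules, then tests whether other protocol text closes the gap.

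**1. What each section does with each screening result**

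| Screening result | Section 4.6.1 | Section 5.2 |
|---|---|---|
| TB test positive, x-ray not clear | excluded | excluded (criterion 3) |
| TB test positive, x-ray clear, no TB history | excluded | may enter at joint discretion, untreated (criterion 3) |
| TB test indeterminate twice | not addressed | excluded; no x-ray route (criterion 3) |
| Hepatitis B core antibody present | not separately addressed | excluded; no exception (criterion 24) |

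The second row is the conflict. The third shows that criterion 3 is also uneven within itself: two indeterminate results bar a subject, while a positive result with a clear x-ray need not. The fourth shows that, where the protocol gives unknown immunosuppression as its reason, it excludes on a marker alone.

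**2. Does other text close the gap?**
- The TB-history bullet does not reach a subject with a positive test and no history.
- The x-ray looks for pulmonary disease, current or past. It adds no treatment.
- The permitted and prohibited medication tables, the laboratory table and the Time and Events Table contain no TB preventive-treatment requirement.
- The suppressive-therapy bullet may work the wrong way, because it can be read as barring a subject already on preventive treatment.

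**3. What protection remains after entry?** In the current Time and Events Table, vital signs including temperature are taken at every site visit. A physical examination is done at every site visit except Day 8. The brief examination covers the lungs, and the full one covers the respiratory system and lymph nodes. Section 4.6.1 adds monitoring for signs of infection. Section 5.4.1 stops treatment for a serious opportunistic or atypical infection, and Section 5.4.2 provides Safety Review Team review. None of these is specific to TB, and the stopping rule acts only once infection has developed.

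**4. Is the wording current?** Sections 4.6.1 and 5.2 are available only as in the original protocol. The visible Section 5.2 amendment entries change the contraindications (Amendment 1) and criterion 23 (Amendments 3 and 4). The visible Section 4.6.1 entry changes the drug-interaction row (Amendment 1). None of the four amendment summaries mentions TB, though those for Amendments 1 to 3 also refer to unspecified minor clarifications. Parts of the log for Amendments 2 and 3 are not available, including places where changes to these sections could sit. Carry-forward is therefore likely but not confirmed.

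**The case against.** The strongest reply is that both halves of the conflict come from superseded text, and the missing parts of the log could hold a correction. That stands. It limits the point to a conditional one, and a reader should not infer that the protocol in force certainly contains the conflict.

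A second reply is that Section 4.6.1 is a summary and Section 5.2 is the binding rule, so sites face no ambiguity. That is true for sites, but it does not help. The binding rule is the one that omits the protection, and the summary is what the benefit:risk conclusion rests on.

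Third, entry is gated. A reader might infer that a site can waive the TB exclusion alone. It cannot: the x-ray must be clear, and the sponsor's Medical Monitor shares the discretion. Inclusion 2 and the general infection bullet of exclusion 3 also let the Investigator refuse, and nothing shown stops the two from making treatment a condition. All this stands, but it leaves the safeguard to case-by-case judgement.

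Fourth, a reader might take TB testing at screening only to mean that nothing would detect infection later. The documents do not support that, given the temperature checks, examinations and stopping rule. Repeating the test in someone already positive would not address the exception either.

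Finally, hepatitis B core antibody and a TB test mark different infections. The comparison shows uneven reasoning within the protocol, not equal risk.

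**Conclusion.** In the text shown, the inconsistency is real: Section 4.6.1 claims a protection that exclusion 3 can set aside without requiring anything in its place, and exclusion 3 is out of line with its own indeterminate-test rule and with criterion 24. Because it concerns a patient-safety measure that the protocol itself claims, it deserves an amendment and not just a wording note, provided the text is still current.

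Its size cannot be stated. The documents give no test-positive rate and no TB risk, so neither the number admitted nor the chance of a TB event can be derived. It would go too far to conclude that any subject was admitted this way or faces a particular risk. The conclusion assumes that the pre-amendment text of both sections was carried forward.

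**What to change.** First check the current Sections 4.6.1 and 5.2. If the exception has already been removed, nothing is needed.

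If it is still there, the preferred change is to delete the x-ray sentence from exclusion 3, so that a positive QuantiFERON or T-spot test excludes, as Section 4.6.1 says. The cost is one sentence in an amendment and no new test. Each test-positive subject excluded must be replaced by another eligible subject, and the documents do not show how many that would be.

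If the sponsor keeps the exception, three changes are needed together: require preventive treatment before dosing; state that this treatment is not barred by the suppressive-therapy bullet; and describe the exception in Section 4.6.1. The treatment condition would also have to be fitted to the 30-day screening window.
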